## 16.6. OTHER SAFETY ASSESSMENTS

### 16.6.1. BARNES AKATHISIA RATING SCALE (BARS)

The BARS is a rating scale, measuring the observable, restless movements that characterize akathisia. It consists of 4 items: objective restlessness, awareness of restlessness, distress related to restlessness and global clinical assessment of akathisia. Each item is on a 4-point scale 0 to 3, except for the global clinical assessment which is on a 6-point scale 0 to 5, both using low values to represent absence of akathisia and high representing severe akathisia. The BARS total score is the sum of items 1 through 3 and ranges from 0 to 9. Higher values of the BARS total score indicate akathisia is higher in severity. If one or more items at a visit are missing, the total score will not be calculated.

The observed and change from baseline in BARS total scores will be summarized by treatment and visit.

---

**16.6.2. ABNORMAL INVOLUNTARY MOVEMENT SCALE (AIMS)**

The AIMS is a clinician rated assessment of abnormal movements. It contains items related to: facial and oral movements; extremity movements; trunk movements; global judgments; and dental status. Seven items of the AIMS range from 0= “None” to 4= “Severe”. A score of “mild” (2) in two or more categories or a score of “moderate” or “severe” in any one category results in a positive AIMS score (i.e. the scores are not averaged). The global severity score is the response to “Severity of abnormal movements” found within the global judgments section. Additionally, overall severity is scored on the basis of severity of abnormal movements and incapacitation due to abnormal movements.

The (non-global) AIMS total score is the sum of items 1 through 7. The possible range for the AIMS total score is 0 to 28. Higher values of the total AIMS score indicate increased severity in abnormal movement. If one or more of the AIMS total score items are missing at a visit, the score will be set to missing.

The observed and change from baseline in AIMS total scores will be summarized by treatment and visit.

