4.1.1 Part A Inclusion Criteria

Each patient must meet all of the following criteria to be enrolled in this study:

1. Is capable of understanding the written informed consent, provides signed and witnessed written informed consent, and agrees to comply with protocol requirements.
2. Is between the ages of 18 and 75 years, inclusive, at the start of screening (both male and female patients are to be included).
3. Meets the Diagnostic and Statistical Manual of Mental Disorder, 5th Edition (DSM-5) criteria for Bipolar I or Bipolar II Disorder as confirmed by the investigator or sponsor-approved expert site-based rater by a Structured Clinical Interview for DSM-5 Disorders – Clinical Trials Version (SCID-5-CT) and meeting all of the following 5 criteria:

- a. The start of the current MDE is at least 2 weeks but no more than 6 months prior to the screening visit;
- b. Appropriate severity of illness, at least moderately ill, as measured by a rater-administered MADRS total score ≥ 20 and corresponding to a CGI-BP-S score of ≥ 4 at the screening and baseline visits;
- c. Sufficient history and/or independent report (such as family member or outside practitioner) verifying that the current MDE is causing clinically significant distress or impairment in social, occupational, or other important areas of functioning;
- d. A lifetime history of at least 1 bipolar manic episode or mixed episode (for Bipolar I) or hypomanic episode (for Bipolar II);
- e. A rater-administered YMRS total score of ≤ 12 at the screening and baseline visits. The presence of psychotic symptoms may result in an increased YMRS without evidence of mania/hypomania. Therefore, a patient with a YMRS > 12 AND psychotic symptoms may be included pending adjudication review for diagnostic certainty of the depressive episode.

4. Has a body mass index (BMI) of 18 – 35 kg/m², inclusive.
5. Either must agree to use highly effective methods of birth control (defined as those, alone or in combination, that result in a failure rate less than 1 percent per year when used consistently and correctly) for at least 2 weeks prior to randomization (starting with signing informed consent) through to the end-of-study follow-up visit or must be of non-childbearing potential (defined as either permanently sterilized or, if female, post-menopausal; the latter is defined as at least 1 year with no menses without an alternative medical explanation).

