6.3.2.4 Barnes Akathisia Rating Scale

The BARS is a rating scale for drug-induced akathisia developed by Barnes (1989). It includes the rating of observable restless movements, the subjective awareness of restlessness, and the distress associated with the akathisia. There is also a global rating for severity. The scale is completed by the investigator or an expert site-based rater after a standard examination. Objective akathisia, subjective awareness and subjective distress are rated on a 4-point scale from 0 to 3, yielding a total score from 0 to 9. The Global Clinical Assessment of Akathisia is rated separately, on a 5-point scale from 0 to 4. The BARS is to be completed at baseline and periodically throughout the study as specified in the schedule of events (Table 6–1 and Table 6-2 for Parts A and B, respectively).

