**16.6.4. YOUNG MANIA RATING SCALE (YMRS)**

The YMRS is an 11-item, clinician-administered mania rating scale with established reliability, validity, and sensitivity that was designed to assess the severity of manic symptoms. Four of the YMRS items are rated on a 0 to 8 scale, with the remaining 7 items rated on a 0 to 4 scale. The total score is the sum of all 11 items and ranges from 0 to 60. The total score is appropriate both for assessing baseline severity of manic symptoms and for assessing treatment-emergent manic symptoms in subjects with Bipolar I or Bipolar II Disorder with depression. It will be completed by the investigator or an expert site-based rater.

The observed and change from baseline in YMRS total score will be summarized by treatment and visit.

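### No visible safety table counts the patients who newly become cases on the AIMS, YMRS or BARS; by-visit summaries of total scores cannot supply that number

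*SAP*

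**What the plan says.** **AIMS.** SAP 16.6.2, like Protocol 6.3.2.3, calls a patient positive with a mild rating in at least two areas, or a moderate or severe rating in one; this "results in a positive AIMS score (i.e. the scores are not averaged"). The planned output is: "The observed and change from baseline in AIMS total scores will be summarized by treatment and visit".

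**YMRS.** SAP 16.6.4 says the total score suits the assessment of manic symptoms that emerge on treatment. The planned output is: "The observed and change from baseline in YMRS total score will be summarized by treatment and visit". Protocol 4.1.1 sets the entry condition: "A rater-administered YMRS total score of ≤ 12 at the screening and baseline visits". It also allows an exception: "a patient with a YMRS > 12 AND psychotic symptoms may be included pending adjudication review".

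**BARS.** SAP 16.6.1 plans: "The observed and change from baseline in BARS total scores will be summarized by treatment and visit". The global akathisia rating is named among the baseline safety characteristics in SAP 11, and in no visible post-baseline output. The SAP describes the item scales as 0 to 3, "except for the global clinical assessment which is on a 6-point scale 0 to 5". Protocol 6.3.2.4 says: "The Global Clinical Assessment of Akathisia is rated separately, on a 5-point scale from 0 to 4".

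**What a summary contains.** Under SAP 8, continuous variables get n, mean, SD, median, minimum and maximum, and source data are listed. SAP 16 adds a last on-treatment value.

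**Per-patient counts elsewhere.** SAP 16.2 to 16.4 plan incidence or shift tables against markedly abnormal limits for laboratory tests, ECG and vital signs. SAP 16.6.5 counts patients with emergent or worsened suicidal ideation. SAP 16.1.1 gives incidence of every treatment-emergent event by preferred term, with relative risks. SAP 16.1.3 counts patients with an extrapyramidal event, using the narrow and broad standard query.

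**The concern.** New dyskinesia, akathisia and switch to mania are expected in a minority of patients. The natural safety question is how many patients per arm became cases at any time on treatment. The scales are administered on a schedule so that cases are found without relying on spontaneous report. A by-visit summary of a total score does not answer that question, and cases that arise at different visits are never combined into one count. For the AIMS the plan already holds the rule that would give the count. What is at stake is the between-arm reading of mood and movement safety; no efficacy conclusion is affected.

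**Working it through.** **1. Denominator.** The documents state no case rate for these scales, so the only figure to reproduce is arm size (Protocol 7.2). With a difference of 3, SD 7.5, Bonferroni two-sided 0.025 per dose and 90% power, the normal-approximation formula gives 156 per arm. At the stated 157, power is 90.4% (90.1% by noncentral t). Allowing for 14% loss, 157/0.86 = 182.6, so 183 per arm. The plan's 157 and 183 reproduce. The Safety Set is dosed patients, so 183 is an upper bound; at 157 the shifts below are larger by 183/157 = 1.17.

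**2. Formula and assumptions.** Shift in arm mean = (number of cases × rise per case) / 183, all other patients unchanged. Case numbers and rises are my assumptions. For the AIMS, +3 is the smallest rise that makes a patient positive from a zero baseline (one item from none to moderate).

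| Scale (range of total) | Rise per case | 3 cases | 5 cases (2.7%) | 10 cases |
|---|---|---|---|---|
| AIMS (0–28) | +3 | 9/183 = 0.05 | 15/183 = 0.08 | 30/183 = 0.16 |
| BARS (0–9) | +4 | 12/183 = 0.07 | 20/183 = 0.11 | 40/183 = 0.22 |
| YMRS (0–60) | +10 | 30/183 = 0.16 | 50/183 = 0.27 | 100/183 = 0.55 |
| YMRS (0–60) | +15 | 45/183 = 0.25 | 75/183 = 0.41 | 150/183 = 0.82 |

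**3. The other planned statistics.** In every row the median change is 0. The maximum equals the rise per case whether there are 3 cases or 10, so it shows that a case exists but not how many.

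**4. Between arms.** Suppose switchers rise 15 YMRS points while everyone else falls 1 in both arms. Five switchers then shift the difference in means by 16 × 5/183 = 0.44. With an assumed SD of change of 3 to 5, the standard error of the difference, SD × √(2/183), is 0.31 to 0.52. Power to detect the shift at two-sided 0.05 is 29% down to 13%. With 10 switchers the shift is 0.87 and power is 80% down to 39%. As counts, 5/183 against 0/183 gives Fisher p = 0.061, and 10/183 against 1/183 gives p = 0.011. These tests are yardsticks only, since the SAP plans none on the scales.

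**5. Does adverse-event reporting fill the gap?** Protocol 6.5 asks for clinically significant safety assessments, including worsening from baseline, to be recorded as adverse events. It then exempts findings attributed to the underlying disease unless they are worse than expected for the patient. Dyskinesia and akathisia should mostly pass that filter. A YMRS rise in a bipolar patient may not, although Protocol 6.3.1.1 counts worsening of the treated condition as an adverse event. No mania or hypomania grouping is visible in SAP 16.1; elevated mood and mood disturbance appear as a group only in the abuse-related list of SAP 16.1.4.

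**The case against.** The strongest reply is that cases stay visible and are partly counted already. Minimum, maximum and listings would expose an extreme patient. Extrapyramidal and other adverse events are counted per patient, and SAP 16.1.1 compares arms by relative risk, confidence interval and chi-square test. The SAP also follows Protocol 7.5.8, which asks for the same scale summaries. All of this stands, and it limits the point to a missing count.

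A reader might infer more than the documents support:

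- *That the scales are analysed only as means, so cases vanish.* SAP 8 rules this out.
- *That the AIMS section contradicts itself by averaging scores it says are not averaged.* The phrase concerns item ratings within one patient and does not forbid a mean across patients. The rule is unused, not violated.
- *That switches could appear as improvement.* If 5% of an arm rise 15 points and 95% fall 1, the arm mean is 0.05 × 15 − 0.95 × 1 = −0.20. But if placebo patients fall 1 with no switchers, the difference is −0.20 − (−1) = +0.80, in the adverse direction.
- *That a YMRS above 12 is a mood switch.* Neither document says so. Twelve is an entry limit, the protocol notes that psychotic symptoms can raise the score without mania, and a move from 12 to 13 would cross it.
- *That the BARS range conflict distorts planned results.* The total is 0 to 9 in both documents. The conflict touches only the global item, which is visibly used at baseline alone.

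The table shells mentioned in SAP 8 are not available and might already contain such counts. Against that, SAP 16.6.1 to 16.6.4 show no redaction marks, and each section ends with its planned output.

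**Conclusion.** The point holds as a gap in descriptive safety reporting. The visible plan gives no per-patient count of new cases on the AIMS, YMRS or BARS, although it has an AIMS case rule and plans such counts for other safety data. The gap is narrower for movement disorder, where adverse-event tables count reported cases, and widest for mood switch. A handful of cases moves an arm mean by roughly 0.1 point on the AIMS or BARS and a few tenths on the YMRS. These sizes rest on assumed case numbers and rises; the absence of a count does not. A change is worth making because it is cheap and improves detection, but the primary and key secondary analyses are untouched.

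**What to change.** Check the table shells first. If the counts are not there, add to SAP 16.6, by treatment group on the Safety Set:

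- **AIMS:** number and percentage positive at any post-baseline visit among patients not positive at baseline, by the rule in SAP 16.6.2.
- **YMRS:** number and percentage above 12 at any post-baseline visit among patients at 12 or less at baseline, labelled as a descriptive threshold taken from the entry limit and not as a diagnosis of mood switch. The baseline restriction deals with patients admitted under the psychotic-symptom exception.
- **BARS:** a shift table of the global rating from baseline to worst post-baseline value. Before it is programmed, reconcile the two stated ranges (0 to 4 in Protocol 6.3.2.4, 0 to 5 in SAP 16.6.1) with the form in use.

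All three use data already collected and need no new visit or assessment. The cost is a few more descriptive safety tables and one range correction.

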**16.6.3. SIMPSON-ANGUS SCALE (SAS)**

The SAS is a measure of extrapyramidal side effects consisting of 10 items: gait, arm dropping, shoulder shaking, elbow rigidity, wrist rigidity, leg pendulousness, head rotation, glabella tap, tremor, and salivation. Items are rated on a scale from 0 (normal) to 4 (extreme in severity). The SAS total score is defined as the sum of all 10 items and ranges between 0 and 40. Lower values of the SAS total score indicate milder symptoms. If one or more items are missing at a visit the SAS total score will be set to missing.

The observed and change from baseline in SAS total scores will be summarized by treatment and visit.

**16.6.4. YOUNG MANIA RATING SCALE (YMRS)**

The YMRS is an 11-item, clinician-administered mania rating scale with established reliability, validity, and sensitivity that was designed to assess the severity of manic symptoms. Four of the YMRS items are rated on a 0 to 8 scale, with the remaining 7 items rated on a 0 to 4 scale. The total score is the sum of all 11 items and ranges from 0 to 60. The total score is appropriate both for assessing baseline severity of manic symptoms and for assessing treatment-emergent manic symptoms in subjects with Bipolar I or Bipolar II Disorder with depression. It will be completed by the investigator or an expert site-based rater.

The observed and change from baseline in YMRS total score will be summarized by treatment and visit.

**16.6.5. COLUMBIA SUICIDE SEVERITY RATING SCALE (C-SSRS)**

The C-SSRS is an instrument designed to systematically assess and track suicidal behavior and suicidal ideation throughout the trial. The C-SSRS includes the following four sections: Suicidal Ideation, Ideation Intensity, Suicidal Behavior, and Actual Suicide Attempts. The strength of this suicide classification system is in its ability to accurately and comprehensively assess suicidality, while limiting the over-identification of suicidal behavior. The C-SSRS will be administered by the investigator or an expert site-based rater.

Suicidal Ideation is assessed by 5 questions, the responses to which equate to a 6-point scale from 0="No ideation present" to 5="Active ideation with plan and intent". A score of 4 or 5 on this scale indicates serious suicidal ideation. Any score greater than 0 will be counted as having suicidal ideation.

The Ideation Intensity total score is the sum of five items from the Ideation Intensity scale: frequency, duration, controllability, deterrents, and reasons for ideation. If a subject did not endorse any suicidal ideation, a score of 0 for the intensity total score will be given. The possible range for the Intensity total score is 0 to 25.

The number and percentage of subjects with each type of suicidal ideation or any suicidal ideation during each study period will be summarized. The most severe ideation, the ideation intensity items (frequency, duration, controllability, deterrents, and reasons for ideation), and the ideation intensity total score will also be summarized descriptively.

Suicidal Behavior is collected as actual attempt, non-suicidal self-injurious behaviour, interrupted attempt, aborted attempt, preparatory acts or behavior, suicidal behavior, and suicide. The number and percentage of subjects with each type of suicidal attempt (actual attempts, interrupted attempts, aborted attempts, and preparatory acts or behavior) will be summarized for each scheduled visit and overall by study period. The number and percentage of subjects with any suicidal behavior and those completing suicide will also be summarized for each scheduled visit and overall by study period.

The number and percentage of subjects with suicidality as measured by the C-SSRS will be summarized, where suicidality is defined as having at least one occurrence of suicidal ideation or at least one occurrence of suicidal behavior. The suicidality indicator will be set to 1 if the subject exhibits suicidality for each visit, 0 if the subject does not exhibit suicidality, and missing otherwise. This data will be summarized at each scheduled visit and overall by study period (treatment and post-treatment).

Data collected on actual suicide attempts (lethality of actual attempts and potential lethality of attempts) will be presented in a data listing.

An overall summary of C-SSRS data (post-Baseline data across all scheduled visits) will include the frequency and percentage of the following:

- At least one suicidal ideation post-Baseline
- Emergence of suicidal ideation (no suicidal ideation at Baseline, and any type of suicidal ideation post-Baseline)
- Emergence of serious suicidal ideation (no suicidal ideation at Baseline, and any serious suicidal ideation [ideation score of 4 or 5] post-Baseline)
- Most severe type of ideation post-Baseline
- Worsening of suicidal ideation (most severe suicidal ideation post-Baseline was more severe than it was at Baseline)
- At least one suicidal behavior post-Baseline
- Emergence of suicidal behavior (no suicidal behavior at Baseline, and any type of suicidal behavior post-Baseline)
- At least one actual attempt post-Baseline
- At least one interrupted attempt post-Baseline
- At least one aborted attempt post-Baseline
- At least one preparatory acts or behaviors post-Baseline
- At least one instance of suicidality [any ideation or behavior] post-Baseline
- Emergence of suicidality (no suicidality at Baseline, and any suicidality post-Baseline)
- Any completed suicides post-Baseline

[REDACTED]

[REDACTED]

[REDACTED]

[REDACTED]

---

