6.1.13 Columbia Suicide Severity Rating Scale

The C-SSRS is a questionnaire developed and validated by Kelly Posner and colleagues (2011) for the assessment of suicidal ideation and behavior. Several versions have been developed including the “Baseline” and “Screening” versions and a combined “Baseline/Screening” version of the scale which assesses suicidal ideation and behavior in a patient’s lifetime and during a predefined time period. This version can assess a patient’s lifetime suicidality as well as eligibility based on inclusion/exclusion criteria. A separate “Since Last Visit” version of the scale has been developed which is used to assess suicidality since the patient’s last visit. This version is meant to assess patients who have completed at least 1 initial C-SSRS assessment, and should be used in every subsequent visit. The “Since Last Visit” version of the C-SSRS addresses any suicidal thoughts or behaviors the patient/participant may have had since the last time the C-SSRS was administered.

In Part A, the C-SSRS will be administered by the investigator or an expert site-based rater, as indicated in the Schedules of Events (Table 6-1 and Table 6-2 for Parts A and B, respectively). In Part B, on Days 75, 125, and 150, the C-SSRS will be administered via telephone by a qualified site-based rater. Concerns for participant safety after phone interviews should be addressed immediately by the investigator.

At screening a potential study participant will not be eligible if he or she reports suicidal ideation of type 4 or 5 on the C-SSRS within 6 months prior to screening or any suicidal behavior in the last 2 years prior to screening, as indicated by any “yes” answers on the suicidal behavior section of the C-SSRS.

[Note: For Part B, all C-SSRS assessments used should be the “Since Last Visit” version, since the patient has had an initial assessment at the Part A Screening Visit.]

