## **7. GENERAL CONSIDERATIONS**

Relative Study Day will be calculated from the date of Day 1, which is the day of first treatment with double-blind study medication in Part A, and will be used to show the start and/or stop days of treatment, study procedures and assessments, prior, concomitant, and post-treatment medications, and adverse events.

[figure not shown]
- If the date of the treatment, procedure, or event is on or after Day 1 date then:

Relative Study Day = (date of variable of interest – Day 1 date) + 1.

- If the date of the treatment, procedure, or event is prior to the Day 1 date then:

Relative Study Day = (date of variable of interest – Day 1 date).

In the situation where the date is partial or missing, Relative Study Day, and any corresponding event durations will appear missing in the listings.

Analyses presented by visit or study day will be based on the scheduled visits as planned in the protocol. Visit windows for unscheduled visits or early discontinuation visits are defined in **Table A**, which provides the mapping of relative day ranges to the scheduled target days and the study periods for Part A. If more than one assessment is available in the same ‘Range of Relative Study Days’ (window), the assessment closest to the Scheduled Target Day will be selected and assigned to the Scheduled Target Day. If two or more assessments are available in the same window and are equidistant from the Scheduled Target Day, the latest assessment will be selected (if before study Part B start). 

Listings will include scheduled, unscheduled, retest and early discontinuation data.

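### The overall C-SSRS summary is limited to scheduled visits, so suicidal ideation or behavior recorded at an unscheduled or early-termination visit can drop out of its emergence and worsening rows.

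*SAP*

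**What the plan says.** SAP 16.6.5 introduces the overall table with "An overall summary of C-SSRS data (post-Baseline data across all scheduled visits) will include the frequency and percentage of the following". The rows are worded as any or worst post-baseline findings. One reads "Emergence of suicidal ideation (no suicidal ideation at Baseline, and any type of suicidal ideation post-Baseline" and another "Worsening of suicidal ideation (most severe suicidal ideation post-Baseline was more severe than it was at Baseline". Similar emergence rows cover serious ideation, suicidal behavior and suicidality.

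On recall, Protocol 6.1.13 says of the since-last-visit version: "This version is meant to assess patients who have completed at least 1 initial C-SSRS assessment, and should be used in every subsequent visit". The same section says that this version "addresses any suicidal thoughts or behaviors the patient/participant may have had since the last time the C-SSRS was administered". Protocol 6.3.2.1 plans the scale at screening, baseline and each later scheduled clinic visit.

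On extra visits, SAP section 7 says: "Visit windows for unscheduled visits or early discontinuation visits are defined in" Table A. When a window holds more than one assessment, "the assessment closest to the Scheduled Target Day will be selected and assigned to the Scheduled Target Day", and ties go to the latest. The section introduces these rules for analyses presented by visit or study day. It also says that listings will hold unscheduled and early-discontinuation data.

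Elsewhere in SAP 16.6.5, ideation, attempts, behavior, completed suicide and suicidality are summarized by study period. No limit to scheduled visits is stated for those period counts.

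**The concern.** The emergence and worsening rows promise any, or the most severe, post-baseline finding for each patient. The stated data source does not guarantee that. Because each C-SSRS covers only the interval since the one before it, a C-SSRS at an extra visit closes off that interval. If that record is then left out, no later record covers the same days, and the event is in no row of the overall table.

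At stake is the count of patients with new or worse suicidality in a depression trial. No other visible table gives the four emergence rows (ideation, serious ideation, behavior, suicidality) or the worsening row. A second consequence is that the period counts and the overall table could show different numbers for the same category, such as actual attempts.

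**Working it through.** The plan states no figure to reproduce. The check sets the rules against each other and then enumerates the selection rule.

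**Inputs.** Table A windows and target days (SAP section 7): Days 2–11 for Day 8, 12–18 for Day 15, 19–25 for Day 22, 26–32 for Day 29 and 33–39 for Day 36. Selection rule: closest to target, ties to the latest. Recall: since the previous administration. How far the scheduled visit falls from its target day is my assumption, shown from 0 to 3 days either way.

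**Reading 1: the overall table takes scheduled visits literally.** Every unscheduled C-SSRS record is outside the table, whatever its date.

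**Reading 2: the section 7 windows apply.** Let t be the target day, s the scheduled visit and u an unscheduled C-SSRS in the same window. The unscheduled record is kept if |u − t| < |s − t|, or if the distances are equal and u > s. Otherwise it is dropped.

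The five windows hold 10 + 7 + 7 + 7 + 7 = 38 days. Removing one scheduled day from each leaves 33 possible days for u. For a scheduled visit k days late, 2k − 1 days per window are kept; for one k days early, 2k days, because the tie then goes to the later record. Days lost are 33 − 5(2k − 1) and 33 − 5(2k).

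| Scheduled visit | Unscheduled days lost |
|---|---|
| on target | 33/33 (100%) |
| 1 day late | 28/33 (85%) |
| 1 day early | 23/33 (70%) |
| 2 days late | 18/33 (55%) |
| 2 days early | 13/33 (39%) |
| 3 days late | 8/33 (24%) |
| 3 days early | 3/33 (9%) |
| missed, one unscheduled record | 0/38 (0%) |

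These are shares of calendar days, not probabilities that an event is lost.

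**Example of loss.** Day 15 scheduled: none. Day 18 unscheduled: attempt. Day 22 scheduled: none since Day 18. Day 18 lies in the window for Day 15 at distance 3; the Day 15 record has distance 0 and is kept. Day 22 looks back only to Day 18. The attempt is in no row of the overall table.

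**Reverse loss.** Suppose the Day 22 visit is held on Day 24 and is positive for the days since an unscheduled, negative C-SSRS on Day 21. Day 21 is at distance 1 and Day 24 at distance 2, so the negative record is kept. The next scheduled visit looks back only to Day 24.

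**Early termination.** Scheduled Day 22 negative, early termination on Day 25 positive: the distances are 0 and 3, so the early-termination record is dropped, and a follow-up C-SSRS would look back only to Day 25. That this visit includes a C-SSRS is inferred from Protocol 4.2.2, which asks for all end-of-study assessments where possible; the schedule table is not legible.

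**After the change.** If the table uses all post-baseline records, with the worst for ideation and any occurrence for behavior, no record is lost under any visit timing.

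**The case against.** The strongest case on the other side is that the loss is conditional and the events are not hidden. Several parts of it stand.

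- A reader might infer that every event at an unscheduled visit disappears. Under the section 7 windows that is not so: a record that is alone or closest in its window is kept. Section 7 ties its rule to displays by visit or study day, so it is also unclear whether the rule governs this table at all.
- A reader might infer that lost events survive only in listings. The period counts of ideation, attempts, behavior, completed suicide and suicidality state no scheduled-visit limit and may include them. Events reported as adverse events also reach the adverse event summaries (SAP 16.1). Only emergence and worsening have no other visible table.
- The mechanism needs a C-SSRS at the extra visit. The legible text plans the scale at scheduled clinic visits. If an unscheduled contact has no C-SSRS, the next scheduled one covers that interval and nothing is lost.
- A reader might infer that the completed-suicide row is empty because of the word scheduled. It is not: a patient who has died attends no visit of any kind, and SAP 16.1.2 lists deaths from the adverse event, end-of-treatment and completion/withdrawal pages.
- A reader might infer that the loss falls mainly on the most serious events. The documents contain nothing on where acute suicidality is recorded.
- Redacted text follows the list in SAP 16.6.5, and the table shells are not among the documents. Either might bear on this; nothing is inferred from them.

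What the objection does not remove is that neither reading of the visible text delivers the worst post-baseline value that the rows describe.

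**Conclusion.** The point holds in conditional form. If a C-SSRS is given at an unscheduled or early-termination visit, an event recorded there can be missing from the emergence and worsening rows. On the literal reading of SAP 16.6.5, an unscheduled record is always left out. If the section 7 windows apply, it is left out whenever another record in the window is closer to the target day or wins the tie, and a scheduled positive record can be displaced in the same way.

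The number of patients affected cannot be estimated, because the documents give neither the rate of unscheduled C-SSRS records nor that of suicidal events. For scale only, one patient is 1/183 = 0.55 percentage points of an arm at the planned randomized size; that is not an estimate of loss.

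The table is descriptive and has no bearing on the efficacy conclusions. The severity is should-fix: the rule can give wrong counts in a safety display that nothing else visible supplies, and the data to correct it are already collected.

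**What to change.** In SAP 16.6.5, replace the scheduled-visit limit on the overall summary with a statement to this effect: the overall summary uses all post-baseline C-SSRS records in the study period, whether scheduled, unscheduled or early termination; ideation rows use the worst record per patient, and behavior rows count any occurrence. Add that the one-record-per-window rule of section 7 applies to by-visit C-SSRS displays only. State the same data source for the by-study-period counts, so that the tables agree.

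The cost is a short SAP edit and a small programming change. No new data are needed, and the by-visit displays are unchanged.
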